### 6.13.2.3. Pancreatitis

Summaries of adjudicated and investigator-reported pancreatic events will be provided by treatment. Determination of investigator-reported events will be through the predefined Standardized MedDRA Queries (SMQ) search for acute pancreatitis and MedDRA PT of pancreatitis chronic. Detailed searching criteria can be found in [Appendix 1](#). Treatment-emergent adjudication-confirmed pancreatitis will be considered an AESI.

#### 6.13.2.3.1. Pancreatic Enzyme Assessment

Observed pancreatic enzyme data (p-amylase and lipase) will be summarized by treatment and nominal visit. The number and proportion of patients with pancreatic enzyme values exceeding the following thresholds will be provided by treatment, baseline pancreatic enzyme value ( $\leq$ Upper Limit of Normal [ULN],  $>$ ULN), and nominal visit: ( $>1$  to  $\leq 3$ )  $\times$  ULN, ( $>3$  to  $\leq 5$ )  $\times$  ULN, ( $>5$  to  $\leq 10$ )  $\times$  ULN,  $>10 \times$  ULN.

Additionally, the number and proportion of patients with maximum postbaseline pancreatic enzyme values exceeding the following thresholds will be provided by baseline pancreatic enzyme value ( $\leq$ ULN,  $>$ ULN), and treatment: ( $>1$  to  $\leq 3$ )  $\times$  ULN, ( $>3$  to  $\leq 5$ )  $\times$  ULN, ( $>5$  to  $\leq 10$ )  $\times$  ULN,  $>10 \times$  ULN.

An MMRM analysis will be used to analyze each pancreatic enzyme with a log transformed (postbaseline measure/baseline measure) response variable and stratification factors, treatment, nominal visit, and treatment-by-nominal visit interaction as fixed effects, and baseline value as a covariate.

### 6.13.2.4. Thyroid Malignancies and C-Cell Hyperplasia

Treatment-emergent thyroid malignancies and C-cell hyperplasia will be identified using predefined MedDRA high level terms (HLTs) of thyroid neoplasms malignant and PT of thyroid C-cell hyperplasia. Detailed searching criteria can be found in [Appendix 1](#). A summary by treatment and PT, PT within SMQ, and HLT will be provided. Thyroid malignancies and C-cell hyperplasia will be considered AESIs.

### 6.13.2.5. Malignancies

The AE database will be searched using predefined SMQs to identify events consistent with malignancy. Detailed searching criteria can be found in [Appendix 1](#). A summary by treatment and PT within SMQ and a listing of TEAEs will be provided. Malignancy will be considered an AESI.

#### 6.13.2.5.1. Calcitonin

Observed calcitonin data will be summarized by treatment and nominal visit. Additionally, the number and proportion of patients with a calcitonin value exceeding the following thresholds will be provided by treatment, baseline calcitonin value ( $\leq 20$  ng/L,  $> 20$  ng/L), nominal postbaseline visit, and postbaseline calcitonin categories:  $\leq 20$  ng/L,  $> 20$  ng/L to  $\leq 35$  ng/L,  $> 35$  ng/L to  $\leq 50$  ng/L,  $> 50$  ng/L to  $\leq 100$  ng/L,  $> 100$  ng/L.

Additionally, the number and proportion of patients with a maximum postbaseline calcitonin value exceeding the following thresholds will be provided by treatment and baseline calcitonin value ( $\leq 20$  ng/L,  $> 20$  ng/L):  $\leq 20$  ng/L,  $> 20$  ng/L to  $\leq 50$  ng/L,  $> 50$  ng/L to  $\leq 100$  ng/L  $> 100$  ng/L.

#### 6.13.2.6. Major Adverse Cardiovascular Events (MACE)

Major adverse cardiovascular events reported by investigators are adjudicated by an independent clinical endpoint committee (CEC) in a blinded fashion. The major adverse cardiovascular events (MACE) events of special interest are: deaths due to CV cause, myocardial infarction, hospitalization for unstable angina, hospitalization for heart failure, coronary interventions (such as coronary artery bypass graft [CABG] or percutaneous coronary intervention [PCI]); and cerebrovascular events, including cerebrovascular accident (stroke) and transient ischemic attack (TIA).

A listing of patients reporting MACE events, either reported by investigator or identified by the CEC, will be provided. The listing will include treatment, patient identification including the site number, date of event, type of event as reported by the investigator, type of event as adjudicated by the CEC, time from first dose of study drug to the event, and time from last dose to the event (if patient has discontinued study drug prior to the event). Only adjudication-confirmed MACE will be considered an AESI.

#### 6.13.2.7. Supraventricular Arrhythmias and Cardiac Conduction Disorders

The AE database will be searched using predefined SMQs or MedDRA HLTs to identify events consistent with supraventricular arrhythmias and cardiac conduction disorders. Detailed searching criteria can be found in [Appendix 1](#). Incidence of the resulting TEAEs will be summarized by treatment and PT within SMQ and HLT. Treatment-emergent severe/serious supraventricular arrhythmias and cardiac conduction disorders will be considered AESIs.

#### 6.13.2.8. Hypersensitivity Events

Hypersensitivity reactions and related information reported via the “Hypersensitivity and Anaphylactic Reactions” eCRF will be summarized by treatment. Two main analyses are performed:

- **Potential Immediate Hypersensitivity:** Analysis of TEAEs occurring from the start of study drug administration up to 24 hours after the end of study drug administration. For events without the hypersensitivity CRF, only date (no time) information is collected. Events occurring on the same date as the study drug injection date will be included.

- **Potential Non-Immediate Hypersensitivity:** Analysis of TEAEs occurring more than 24 hours after the end of study drug administration, but prior to subsequent study drug administration.

Summaries of all potential hypersensitivity reactions will be generated by PT with decreasing frequency by treatment. The AE database will be searched using predefined SMQs to identify events consistent with hypersensitivity events. Detailed searching criteria for hypersensitivity events can be found in [Appendix 1](#). Severe/serious hypersensitivity events identified by predefined SMQ searches will be considered AESIs.

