## 5. Study Design

### 5.1. Overall Design

[figure not shown]
Study GPGH is a Phase 3, multicenter, randomized, open-label, parallel-group study that will investigate the effects of treatment with LY3298176 5 mg, 10 mg, and 15 mg QW compared with titrated insulin degludec in patients with T2DM who have inadequate glycemic control on stable doses of metformin, with or without an SGLT-2i. The primary endpoint will be the mean change in HbA1c from baseline to 52 weeks.

Patients should be on a stable dose (no dose change for at least 3 months) metformin alone or metformin plus an SGLT-2i. Patients will be randomized in a 1:1:1:1 ratio (LY3298176 5 mg QW, 10 mg QW, 15 mg QW, or insulin degludec once daily [QD]). Patients will be stratified at randomization based on HbA1c ( $\leq 8.5\%$ ,  $> 8.5\%$  [69 mmol/mol]), country, and use of concomitant oral antidiabetic treatments (metformin alone, metformin plus an SGLT-2i).

Insulin degludec will be injected QD, as a single SC injection, ideally at bedtime at approximately the same time every night. The initial dose will be 10 IU/day and will be adjusted weekly per a treat-to-target (TTT) algorithm, based on the last 3 fasting blood glucose (FBG) values.

Study governance considerations are described in detail in [Appendix 3](#).

[Figure GPGH.1](#) illustrates the study design.

Abbreviations: FBG = fasting blood glucose; QD = once daily; QW = once weekly; SGLT-2i = sodium-glucose co-transporter-2 inhibitor; TTT = treat to target.

a Stable doses of metformin ( $\geq 1500$  mg/day)  $\pm$  SGLT-2i for  $\geq 3$  months prior to Visit 1 and during the screening/lead-in period.

b The starting dose of insulin degludec will be 10 IU/day ideally at bedtime, titrated to a FBG  $< 90$  mg/dL, following a TTT algorithm.

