## 7. Treatments

### 7.1. Treatments Administered

Patients will be randomized in a 1:1:1:1 ratio to receive LY3298176 5 mg, 10 mg, 15 mg, or insulin degludec. LY3298176 will be administered QW as SC injection in patients with T2DM who are already treated with a stable dose of at least 1 and no more than 2 oral antihyperglycemic medications: metformin alone or metformin plus sodium-glucose co-transporter-2 inhibitors.

Table GPGH.3. shows the randomized treatments for the entire treatment period.

The starting dose of LY3298176 will be 2.5 mg QW for 4 weeks, followed by an increase to 5 mg QW, for the duration of the study for the 5-mg group. For the 10-mg group, the starting dose of LY3298176 will be 2.5 mg QW for 4 weeks, then the dose will be increased by 2.5 mg every 4 weeks (2.5 to 5 to 7.5 to 10 mg) until the 10-mg dose is reached and maintained for the duration of the study. For the 15-mg group, the starting dose of LY3298176 will be 2.5 mg QW for 4 weeks, then the dose will be increased by 2.5 mg every 4 weeks (2.5 to 5 to 7.5 to 10 to 12.5 to 15 mg) until the 15-mg dose is reached and maintained for the duration of the study.

The starting dose of insulin degludec will be 10 IU/day at bedtime, titrated to a FBG <90 mg/dL, following a TTT algorithm (Philis-Tsimikas et al. 2013, Pan et al. 2016, Aroda et al. 2016). Patients will titrate the insulin degludec dose in a weekly manner and will make the dose decision with the investigator for the first 8 weeks (phone or clinic visit). For further dose titration, from Week 8 to Week 16, patients will have a phone or clinic visit every other week.

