### 3. Revision History

Statistical analysis plan (SAP) Version 1 was approved prior to the first patient receiving study drug.

The second version was approved prior to the final database lock. The following represent major changes made for the second version:

1. Update definition of analysis set: Per agreement with the US FDA, patients that discontinue study drug due to inadvertent enrollment are excluded from efficacy analysis.
2. Update baseline definition for selected measures based on scientific consideration and to minimize missing values at baseline.
3. Update primary endpoint: Missing data imputation. Corrected the definition of “retrieved dropout.” Use of local lab data for glycemic control measures when central lab data are not available.
4. Update the language to handle lack of convergence in longitudinal logistic regression analysis due to low number of events for hemoglobin A1c (HbA1c) and weight loss target analyses.
5. Update the language in section on adverse events of special interest and renamed section to “Special Safety Topics” to be consistent with the program SAP (see Section 6.13.2).
6. Add section to assess SARS-CoV-2 (COVID-19) impact (see Section 6.20).
7. Add an explanation of the unblinding plan that was created for Study GPGH after the initial approval of this analysis plan.

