There will be 2 estimands of interest in evaluating primary and secondary efficacy objectives. The first estimand, the “efficacy” estimand, represents efficacy prior to discontinuation of study drug without confounding effects of rescue therapy for persistent severe hyperglycemia. Analysis relative to the “efficacy” estimand will be conducted using the efficacy analysis set (EAS). The second estimand, the “treatment-regimen” estimand (including all data), represents the efficacy irrespective of adherence to investigational product or introduction of rescue therapy for persistent severe hyperglycemia. Analyses relative to the “treatment-regimen” estimand will be conducted using the full analysis set (FAS).

Unless specified otherwise, safety analyses will be conducted relative to the “treatment-regimen” estimand using the safety analysis set (SS).

End of study participation for a patient will be the earliest of date of death, date of withdrawal from further participation in the study, or date of safety follow-up visit (Visit 801). For patients considered to be lost-to-follow-up, end of study participation will be the date of lost-to-follow-up reported by the investigator. Patient data included in the database after the last date of study participation (date of early termination or date of safety follow-up) will be excluded from statistical analysis. Listings of such data will be provided.

Summary statistics for categorical measures (including categorized continuous measures) will include sample size, frequency, and percentages. Summary statistics for continuous measures will include sample size, mean, standard deviation (SD), median, minimum, and maximum. The summary statistics will be presented by nominal visit.

Statistical treatment comparisons will only be performed between tirzepatide doses and insulin degludec. Since the trial is not adequately powered to detect difference among tirzepatide doses, comparisons among tirzepatide arms will not be performed unless otherwise specified.

Statistical summaries and results of statistical analyses will be displayed in the following treatment order: 5 mg tirzepatide, 10 mg tirzepatide, 15 mg tirzepatide, insulin degludec.

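### The 24-hour split of hypersensitivity events in SAP 6.13.2.8 cannot be read across arms: at equal adherence the immediate window covers seven times as much on-treatment time with daily degludec as with weekly tirzepatide.

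*SAP*

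**What the plan says.** SAP 6.13.2.8 defines two main analyses of hypersensitivity events, both reported by treatment. The immediate one is "Analysis of TEAEs occurring from the start of study drug administration up to 24 hours after the end of study drug administration". The non-immediate one is "Analysis of TEAEs occurring more than 24 hours after the end of study drug administration, but prior to subsequent study drug administration". Events without the dedicated form carry only a date, and for these the immediate analysis has the rule "Events occurring on the same date as the study drug injection date will be included". Both definitions refer to study drug in general, with no limit to the tirzepatide arms.

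The same section also plans an unsplit display, "Summaries of all potential hypersensitivity reactions will be generated by PT with decreasing frequency by treatment", and treats severe or serious events found by the SMQ search as events of special interest.

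The dosing intervals differ. Protocol 5.1: "Insulin degludec will be injected QD, as a single SC injection". Protocol 7.1: "LY3298176 will be administered QW as SC injection in patients with T2DM".

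SAP 6.13.2.8 names no test. SAP 6.13 makes Fisher's exact test the default for categorical safety data unless something else is specified, and SAP 6.2 adds "Statistical treatment comparisons will only be performed between tirzepatide doses and insulin degludec".

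**The concern.** A 24-hour window means different things under the two schedules. A fully adherent degludec patient is always within 24 hours of a dose, so nearly every on-drug event is immediate whatever its cause. A tirzepatide patient is within 24 hours of a dose for one day in seven, so background events fall mostly into the non-immediate class.

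Read across arms, the immediate table would flatter tirzepatide and the non-immediate table would count against it, even with equal risk. Incidence of allergic and hypersensitivity reactions against degludec is a stated safety objective (SAP 4.4). These two tables are labelled as the main analyses, and the section carries no caveat about dosing interval.

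**Working it through.** The documents give no figure for window coverage, so there is nothing to reproduce.

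**Inputs from the documents.** Dosing interval 24 h for degludec and 168 h for tirzepatide (Protocol 5.1 and 7.1). Compliance threshold of 75% of doses in all arms (SAP 6.10.1 and 6.10.2); this is a threshold for calling a patient compliant, not a floor on adherence. A missed degludec dose is not made up (Protocol 7.2.1.2). Planned arm size 355 (SAP 5.2). Treatment 52 weeks plus 4 weeks of follow-up (Protocol synopsis), that is 56 × 7 = 392 days.

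**Step 1: coverage of the immediate window.** Coverage = share of doses taken × 24 h / interval.

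| Doses taken | Degludec | Tirzepatide | Ratio |
|---|---|---|---|
| 100% | 24/24 = 100% | 24/168 = 14.3% | 7 |
| 75% | 0.75 × 24/24 = 75% | 0.75 × 24/168 = 10.7% | 7 |

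The ratio is 7 at any equal adherence. The date-only rule gives the same shares at full dosing: 7 of 7 dates against 1 of 7. Variation in the time of the degludec dose (assumed SD 0.5 to 2 h) lowers its full-dosing coverage only to 95-99%.

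**Step 2: allow for dose-triggered events.** Let f be the assumed share of events triggered within 24 h of a dose, equal in both arms. Immediate share = f + (1 − f) × coverage. At full dosing it is 1 for degludec and f + (1 − f)/7 for tirzepatide, so with equal true risk the degludec-to-tirzepatide ratio of immediate events is:

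- f = 0: 1/0.143 = 7.0
- f = 0.25: 1/0.357 = 2.8
- f = 0.5: 1/0.571 = 1.75
- f = 0.75: 1/0.786 = 1.27

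**Step 3: expected counts.** Assume 3% incidence in both arms: 355 × 0.03 = 10.65 patients with an event. With f = 0 at full dosing, the immediate class has 10.7 on degludec against 1.5 on tirzepatide, and the non-immediate class 0 against 9.1. With f = 0.5 the figures are 10.7 against 6.1, and 0 against 4.6.

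**Step 4: what the default test would do.** False rejection is the exact sum, over two independent binomials with n = 355, of outcomes with two-sided Fisher p < 0.05. The comparison is one tirzepatide dose against degludec, following SAP 6.2, on a pooled any-event row at full adherence.

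| Assumed incidence | f | Immediate | Non-immediate |
|---|---|---|---|
| 3% | 0 | 70.8% | 89.5% |
| 3% | 0.5 | 14.2% | 30.8% |
| 3% | 0.75 | 5.3% | 2.9% |
| 1% | 0 | 9.8% | 8.7% |

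The unsplit count falsely rejects in 1.5% of trials at 1% incidence and 3.1% at 3%.

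**Step 5: count the time after the last dose.** Step 4 puts every event in an on-drug class, but safety data run through follow-up. Take the last degludec dose at the Week 52 visit and the last tirzepatide dose 7 days before it.

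- Degludec: 365 immediate days and 27 later days (27/392 = 6.9%).
- Tirzepatide: 52 immediate days, 51 × 6 = 306 non-immediate days, and 6 + 28 = 34 later days (34/392 = 8.7%).

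The non-immediate definition requires a later dose, so those later days have no stated class, and I ran both readings. At 3% and f = 0 the expected immediate counts are 10.65 × 365/392 = 9.9 against 10.65 × 52/392 = 1.4, and false rejection is 67%. For the non-immediate class it is 84% if the later days stay unclassified (0 against 10.65 × 306/392 = 8.3). It is 75% if they count as non-immediate (10.65 × 27/392 = 0.7 against 10.65 × 340/392 = 9.2).

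**Step 6: single preferred terms.** At an assumed 0.5% per term, f = 0 and full adherence, with the Step 4 method, false rejection is 0.8% and 0.5%.

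**The case against.** The other side has a good case on consequence. These are descriptive safety tables outside the type 1 error strategy. SAP 6.13.2.8 only summarizes, whereas SAP 6.13.1 and 6.16 state their comparisons explicitly, so Fisher's test reaches this section only through the general default. The high rejection rates need an assumed 3% incidence and no dose-triggered events. That second assumption sits poorly with Protocol 9.2.2.7, which collects the extra data for events judged related to study drug, although events without that form also enter. Rows for single preferred terms would rarely reject. Patients who stop drug early stay in follow-up, which dilutes the contrast further and is not modelled. All of this stands, and it limits the size of the point.

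A reader might go further and infer that the hypersensitivity comparison with degludec is invalid, or that the plan commits to a test with a false-positive rate of 70-90%. The documents support neither. The unsplit summary and the severe/serious SMQ events do not depend on the 24-hour cut, and the three tirzepatide arms share one schedule. The test is a default, not a stated plan, and the 71% and 89% in Step 4 are not bounds to quote because they leave out the time after the last dose.

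What the objection does not remove is the sevenfold difference in coverage. It follows from the dosing intervals alone, and no other section corrects for it.

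**Conclusion.** The point holds as a limited one. As written, the plan yields two by-treatment tables in which dosing interval is mixed with drug effect. The size that rests on the documents alone is the coverage: 100% against 14% at full dosing, 75% against 11% at the compliance threshold, and 7:1 at any equal adherence.

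How far this distorts event counts depends on the dose-triggered share, which the documents do not give. The rejection rates are illustrations. Under the conditions of Step 5 they are about 67% (immediate) and 75-84% (non-immediate) with nothing dose-triggered. Without counting the time after the last dose they are 14% and 31% with half of events dose-triggered, and 10% or less at 1% incidence. The safety objective remains answerable from the unsplit summary and the severe/serious events.

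**What to change.** In SAP 6.13.2.8, do one of the following:

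- show the immediate/non-immediate split for the tirzepatide arms only, by dose, as SAP 6.13.2.10 already does for antibody results; or
- keep the degludec column, add a footnote that the split is not comparable between daily and weekly dosing, and exclude it from the default test in SAP 6.13.

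In both cases, state that the comparison with degludec rests on the already planned unsplit hypersensitivity summary and the severe/serious events.

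The cost is SAP wording and table shells; no new data or analysis is needed. The tirzepatide-only option departs slightly from the program layout, since the special safety section was revised "to be consistent with the program SAP" (SAP 3, Revision History). The footnote option avoids that.

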#### **6.13.2.9. Injection Site Reactions**

Injection site reactions, incidence, and related information reported via the “Injection Site Reactions” eCRF will be summarized by treatment. Information to be summarized includes the location of the reaction, timing of the reaction relative to study drug administration, and characteristics of the injection site reaction: erythema, induration, pain, puritus, and edema.

Additionally, potential injection site reactions will be reported by PT within MedDRA HLTs of injection site reactions, administration site reactions, and infusion-related reactions. Detailed searching criteria for injection site reaction events can be found in [Appendix 1](#). The PT will be used for summary within each HLT category. Only severe/serious injection site reactions will be considered AESIs.

#### **6.13.2.10. Immunogenicity**

Treatment-emergent anti-drug antibodies (TE ADA) are defined as those with a titer 2-fold (1 dilution) greater than the minimum required dilution if no ADAs were detected at baseline (treatment-induced ADA) or those with a 4-fold (2 dilutions) increase in titer compared to baseline if ADAs were detected at baseline (treatment boosted ADA). A patient is evaluable for TE ADA if the patient has a non-missing baseline ADA result, and at least 1 non-missing postbaseline ADA result.

The frequency and percentage of patients with preexisting ADA, with TE ADA, with cross-reactive antibodies, and with neutralizing antibodies will be tabulated by dose, where proportions are relative to the number of patients who are TE ADA evaluable. The frequency and percentage of patients with hypersensitivity and injection site reactions by TE ADA status will be tabulated if warranted by the data.

A listing may be provided of all immunogenicity assessments for those patients who at any time had TE ADA present. This includes the tirzepatide concentration from a simultaneous pharmacokinetic (PK) sample, and the clinical interpretation result.

A listing may be provided for all participants who had ADAs present at any time (including baseline) or had any hypersensitivity or injection site reaction TEAEs.

Depending on the number of patients with TE ADA, selected efficacy and safety subgroup analyses by TE ADA categories may be performed if deemed necessary.

Treatment-emergent ADAs that are associated with AEs of either severe/serious hypersensitivity or severe/serious injection site reactions will be classified as AESIs.

